**Create or insert table to describe the exclusion criteria and methods to ascertain them**

EXCLUSION CRITERIA	METHOD OF ASCERTAINMENT
1. Meets DSM IV criteria for bipolar disorder, schizophrenia or any psychotic disorder other than transient psychosis due to drug abuse. Substance Induced Mood Disorder with Hamilton Depression Scale score $\geq 15$ will be excluded. Patients with Major Depressive Disorder will be eligible to participate, provided they are in remission (Hamilton Depression Scale-25 Score < 8), whether receiving treatment or not.	MINI interview, self-report
2. History of allergic, dermatological, or adverse event related to oxytocin or desmopressin. Patient using oxytocin or vasopressin-based products cannot participate.	Self report
3. Chronic organic mental disorder, insufficient proficiency in English, or any condition or status (illiteracy) that would render an individual incapable of giving informed consent.	Psychiatric evaluation
4. Significant current suicidal risks, suicide attempt within the past year.	Psychiatric evaluation
5. Unstable physical disorders, which might make participation hazardous: hypertension (>140/90), hepatitis (patients with chronic	Medical evaluation

mildly elevated transaminase levels (2-3 X upper limit of normal will be considered acceptable if PT/PTT is normal), serum sodium (Na) < 133 mEq/L, renal failure (creat >2; BUN > 40. History of hyponatremia. Patients on medication (\*) (see partial list below) that may induce hyponatremia will not be excluded, provided no evidence of hyponatremia is found at screening.

6. Coronary vascular disease as indicated by history, or suspected by abnormal ECG. Electrocardiogram, medical history

7. Currently meets DSM-IV criteria for another substance dependence or abuse disorder other than nicotine, or alcohol. If alcohol dependent, must not be in need of detoxification. MINI, medical eval, utox

8. Participants who cannot comply with study procedures during the inpatient or outpatient abstinence induction (phase 1) will not proceed to phase 2. Study performance

9. Pregnancy, positive urine pregnancy test, or breastfeeding. Women who wish to participate must agree to use a method of contraception during the study and sign a written commitment to that effect, and submit to a urine pregnancy test every two weeks of phase 2 History, medical monitoring.

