**Create or insert table to describe the exclusion criteria and methods to ascertain them**

EXCLUSION CRITERIA	METHOD OF ASCERTAINMENT
1. DSM-IV Axis 1 psychiatric diagnosis. Patients with Major Depressive Disorder will be eligible to participate, provided they are in remission (Hamilton Depression Scale Score < 8), whether receiving treatment or not.	MINI interview, self-report
2. Unstable physical disorders, which might make participation hazardous. Serum sodium (Na) < 133 mEq/L, renal failure (creat > 2, BUN > 40) is exclusionary. Patients on medications* (see partial list below) that may cause hyponatremia will not be excluded provided there is no evidence of hyponatremia at screening.	medical and physical examination
3. Diagnosis of Substance Abuse or Dependence disorder, with exception of nicotine dependence. Patients in remission may participate if its duration is greater than 2 years preceding participation.	Self-report, treatment history.
4. History of allergic, dermatological, or adverse event related to oxytocin or desmopressin. Patient using oxytocin or vasopressin-based products cannot participate.	Self-report, medical history.
5. Chronic organic mental disorder, insufficient proficiency in English that would render an individual incapable of giving informed consent.	Psychiatric evaluation
6. History of transphenoidal surgery, sinus surgery in the past month. Simple nasal congestion is not exclusionary.	History, medical screening.

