unsafe; 2) psychiatric worsening, such as emergence of depression (HamD score >17), psychosis (HamD item 22 >3), or of other significant psychiatric symptoms such as suicidality (HamD item 15 > 3), culminating in a CGI score > 6 for two consecutive weeks; 3) substance abuse worsening as assessed by clinicians on the research team during weekly visits, as evidenced by a CGI score >6 for two consecutive weeks; 4) emergence of hyponatremia during the study as indicated by a sodium concentration < 133 mEq/L or early symptoms such as asthenia, fatigue, nausea, vomiting, and weakness; 5) missing one week of supervised clinic-based administration of IN oxytocin or placebo.

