**Criteria for Early Discontinuation**

**Criteria for Early Discontinuation**

Removal from participation from the study can take place under several circumstances: 1) emergence of a medical condition unrelated to the study that would render continued participation unsafe; 2) psychiatric worsening, such as emergence of depression (HamD score >17), psychosis (HamD item 22 >3), or of other significant psychiatric symptoms such as suicidality (HamD item 15 > 3). **Each of these conditions, presenting separately or together, in any combination, which would lead the reviewing clinical to rate a CGI score > 6 for two consecutive weeks;**

3) substance abuse worsening as assessed by clinicians on the research team during weekly visits, as evidenced by a CGI score >6 for two consecutive weeks; 4) emergence of hyponatremia during the study as indicated by a sodium concentration < 133 mEq/L or early symptoms such as asthenia, fatigue, nausea, vomiting, and weakness; 5) missing one week of supervised clinic-based administration of IN oxytocin or placebo. Participation in the study is voluntary and patients can withdraw at any time. In each instance, they will be offered referrals for ongoing treatment.

The study will be stopped if 3 patients develop hyponatremia during the course of the study.

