### **Describe procedures for minimizing risks**

Procedures to minimize risk.

The exclusion criteria are designed to minimize the medical and psychiatric risks to participants. Potential participants will not enter the study should they present with a psychiatric disorder,

---

suicidality risk; except major depression provided it is in remission as attested by a HamD score <8. The baseline medical evaluation includes a history, review of systems, a physical examination, blood chemistry profile including electrolyte (Na, K, Cl, Ca, CO3), liver function test, blood count, urinalysis, urine pregnancy test, and electrocardiogram. It is designed to detect unstable medical conditions that would be prejudicial to participation in the study. Since the most serious potential adverse event is water toxicity and hyponatremia (Na < 133 mEq/L), the screening will focus closely on any signs and symptoms of hyponatremia, which include: nausea, vomiting, headache, confusion, loss of energy, fatigue, restlessness and irritability, muscle weakness, spasms, or cramps, seizures, unconsciousness, and coma. The medical, psychiatric, and laboratory screening is such that hyponatremia, or risks of hyponatremia (medications, renal failure), will be brought forth. Should hyponatremia emerge (Na < 133 mEq/L), whether symptoms are present or not, during the clinical trial, clinic-based and at-home administration of randomized medication will be interrupted, and the patient monitored by daily blood draws to monitor progress, together with encouragement to consume salt containing fluids. Should symptoms and signs appear or worsen, the patient will be referred to an emergency room for electrolyte management. Feeling too relaxed, light-headedness, anxiety, clouded thinking, and nasal cavity irritation are the most common side effects reported in protocols approximating the one presented here (Rodrigues et al., 2009; Ditzen et al., 2009). Symptoms of nasal irritation can occur from nasal administration. We will monitor this during clinic-based administration. This irritation may be more likely in intranasal cocaine users because of pre-existing irritation and damage to the nasal mucosa. No specific intervention is contemplated for this, except that nasal mucosa with preserved olfaction regenerates rapidly. Reduction in consumption or abstinence from cocaine may reduce this problem. Intranasal administration could be a trigger for further cocaine use. The Cocaine Craving Scale will be administered after clinic-based administration. Should cravings be reported, relaxation exercises (as performed in IRB protocol 6013) conducted with the patient by a member of the research staff can assuage the cravings. Whether the intranasal route is itself a trigger in cocaine-dependent patients is an important measure of the feasibility of this approach. The screening, consent, and study visit procedures are designed to safeguard the patient's welfare during their participation. The principal investigator and research staff extensively review and explain procedures, monitor the patient's status to review progress, side-effects, and adverse events. The purpose and procedures of the stress sensitivity testing will be thoroughly explained. Studying stress parameters can help determine if targeting these represents a valid approach to the treatment of cocaine dependence. Post-stress challenge relaxation exercise (already used in Protocol 6013) can help reduce the induced stress. This is especially important for patients choosing the outpatient abstinence induction procedure. We ask patients to give us names of person whom they trust who we can contact during the study should not be able to contact them through their regular number. We emphasize to them that although not mandatory, it is an important safety issue, in case we need to contact them urgently, or reschedule missed appointments. Removal from participation from the study can take place under several circumstances: 1) emergence of a medical condition unrelated to the study that would render continued participation unsafe; 2) psychiatric worsening, such as emergence of depression (HamD score >17), psychosis (HamD item 22 >3), or of other significant psychiatric symptoms such as suicidality (HamD item 15 > 3), culminating in a CGI score > 6 for two consecutive weeks; 3) substance abuse worsening as assessed by clinicians on the research team during weekly visits, as evidenced by a CGI score >6 for two consecutive weeks; 4) emergence of hyponatremia during the study as indicated by a

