
sodium concentration < 130 mEq/L or early symptoms such as asthenia, fatigue, nausea, vomiting, and weakness; 5) missing one week of supervised clinic-based administration of IN oxytoxin or placebo. Participation in the study is voluntary and patients can withdraw at any time. In each instance, they will be offered referrals for ongoing treatment. The study will be stopped if 3 patients develop hyponatremia during the course of the study.

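### Hyponatremia removal criterion: the sodium cut-off is 133 mEq/L in two statements and 130 mEq/L in the third

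*Protocol*

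**What the plan says.** Removal ground 4 appears three times in the protocol.

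- Study Procedures, Phase 2, item 12: "emergence of hyponatremia during the study as indicated by a sodium concentration < 133 mEq/L or early symptoms such as asthenia".
- Criteria for Early Discontinuation: "emergence of hyponatremia during the study as indicated by a sodium concentration < 133 mEq/L or early symptoms such as asthenia, fatigue".
- Describe procedures for minimizing risks: "sodium concentration < 130 mEq/L or early symptoms such as asthenia, fatigue, nausea, vomiting, and weakness".

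Earlier in that same risk section, hyponatremia is twice tied to 133. It is introduced with the words "the most serious potential adverse event is water toxicity and hyponatremia (Na < 133 mEq/L", and the management rule begins "Should hyponatremia emerge (Na < 133 mEq/L), whether symptoms are present or not". The action that follows is that "clinic-based and at-home administration of randomized medication will be interrupted, and the patient monitored by daily blood draws".

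Eligibility uses the same figure. Exclusion item 5 for the cocaine-dependent sample has "serum sodium (Na) < 133 mEq/L", and exclusion item 2 for controls has "Serum sodium (Na) < 133 mEq/L, renal failure (creat > 2, BUN > 40) is exclusionary".

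A study-level stop after three cases of hyponatremia also appears three times: after item 12 in Study Procedures, at the end of Criteria for Early Discontinuation, and at the end of the risk section. None of the three sentences carries a sodium value. The SAP text lists electrolyte monitoring at weeks 2, 4 and 6 but gives no sodium cut-off, so it does not settle the matter.

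**The concern.** The three removal lists are near copies of one another, yet the number that indicates emergent hyponatremia differs in one of them. The protocol names this event as its most serious potential harm and attaches a study-level stop to it. Staff at two clinical sites could look up the criterion in different sections and find different answers for the same laboratory result. The stop shares the weakness in one place: in the risk section it ends the paragraph that contains the 130 figure, and it gives no number of its own to override it.

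**Working it through.** No power or error-rate calculation applies. The check is to set every sodium cut-off in the documents side by side.

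| Protocol location | Use | Cut-off (mEq/L) |
|---|---|---|
| Exclusion criteria, cocaine-dependent sample, item 5 | eligibility | < 133 |
| Exclusion criteria, control sample, item 2 | eligibility | < 133 |
| Study Procedures, Phase 2, item 12, ground 4 | removal | < 133 |
| Criteria for Early Discontinuation, ground 4 | removal | < 133 |
| Procedures for minimizing risks, description of the event | definition | < 133 |
| Procedures for minimizing risks, management | interruption | < 133 |
| Procedures for minimizing risks, ground 4 | removal | < 130 |

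**Count.** There are 7 statements, 6 at 133 and 1 at 130. Among the removal statements alone, 2 of 3 are at 133. The stop is stated 3 times, 0 of them with a cut-off.

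**Affected range.** 133 − 130 = 3 mEq/L. If sodium is reported in whole numbers, the affected results are 130, 131 and 132.

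**Consequence for a patient with none of the listed symptoms:**

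| Sodium (mEq/L) | Removal ground met: item 12 and Early Discontinuation | Removal ground met: minimizing risks | Medication interrupted |
|---|---|---|---|
| 133 or above | no | no | no |
| 130 to < 133 | yes | **no** | yes |
| below 130 | yes | yes | yes |

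Only the middle row is discordant. A patient with the listed early symptoms meets all three versions of ground 4 whatever the sodium, because each version joins the cut-off and the symptoms with *or*.

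**Could 130 be a deliberate second step?** The risk section read alone would allow interruption below 133 and removal below 130. The other two lists exclude this, since both put removal at 133. Nor is 130 presented as a severity grade: ground 4 uses it as the value that shows hyponatremia has emerged, while the same section has already given that value as 133.

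**The stop.** After item 12 and in Criteria for Early Discontinuation, the nearest sodium figure before the stopping sentence is 133. Only in the risk section is it 130.

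**The case against.** The strongest reply is that this is a one-number slip that any reader would resolve to 133 and that changes no required action. Much of that stands.

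- Removal is discretionary. Item 12 says the investigator may remove patients on these grounds, and the other two lists say that removal can take place. In the discordant range, the difference is between having and not having a listed ground for an optional step.
- The mandatory action has a single value. Randomized medication is interrupted and blood drawn daily below 133, with or without symptoms.
- There is a partial backstop. Item 12 removes patients who miss one week of medication. If an ordered interruption counts as missing medication, which the text does not say, a patient interrupted for a week would be removable under every version. The gap would then narrow to symptom-free patients at 130 to below 133 who resume sooner.

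Stronger readings are tempting, but the documents do not support them.

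- A reader might infer that a patient at 131 would be left on drug unmanaged. The interruption rule says otherwise.
- A reader might infer that the three-patient stop has no usable definition. The risk section equates hyponatremia with a sodium below 133 twice, and two of the three stopping sentences follow a 133 criterion. The doubt about the stop is mostly the same slip seen again: once 130 is corrected, 133 is the only sodium figure left.
- A reader might see a conflict between the symptom clause in ground 4 and two other places: the Phase 2 medical review (item 4), which lists similar complaints as usual symptoms, and the risk section's statement that 133 applies with or without symptoms. Neither is a contradiction. Usual symptoms can also serve as a removal ground, and the risk-section statement covers low sodium without symptoms, not symptoms without low sodium.

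The objection does not remove the literal conflict. Near-identical current text carries two values for one safety criterion.

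**Conclusion.** Wrong as written, but minor. The removal cut-off for emergent hyponatremia has two values, and the weight of the text (six statements to one) shows that 133 is intended. The defect reaches only patients with none of the listed symptoms and a sodium of 130 to below 133 mEq/L, and for them only the discretionary removal ground. In the risk section, it also leaves an avoidable doubt about which figure governs the stop. Interruption of medication is unaffected, and no effect on the primary analysis is claimed.

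The documents give no expected frequency of sodium values in this range. How often removal or the stop would turn on the discrepancy therefore cannot be estimated, and no figure is offered. The conclusion rests on the wording of the current protocol, and nothing in the text marks the 130 as redacted or superseded.

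**What to change.** In Describe procedures for minimizing risks, ground 4, change 130 to 133. For consistency, insert (Na < 133 mEq/L) after the word hyponatremia in the stopping sentence at all three places. This is the protocol's own definition, so no new threshold is introduced.

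The investigator may also wish to state whether symptoms without a low sodium count toward the three cases. That is an optional clarification. Limiting the stop to laboratory-confirmed cases, or adding a sodium test when symptoms are reported, is not part of this correction. The first could narrow a safety stop and the second would add a procedure, and both are clinical choices for the investigator.

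The cost is a wording amendment, with no added visits, samples or analyses.

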## **Methods to Protect Confidentiality**

### **Describe methods to protect confidentiality**

We will apply for a certificate of confidentiality for this study (pending).

Patient's records are kept in locked files and released only with the patient's consent. Contact with family members or significant others will only be with the patient's expressed consent. All computer data is stored without names or other coded identification. Data files are protected by passwords. Should data be transmitted electronically, it will be encrypted. Research data will be accessible to the PI, co-PIs, and staff hired to assist with the study. [name] is the sponsor of this study, and holder of the IND (# pending). [name] assumes all responsibility concerning data integrity and confidentiality. The FDA has a right of access to all data gathered during the study as part of their review process. The FDA will also receive an annual report on progress and difficulties encountered during the study. NYSPI, Columbia University, New York state will have access to the data as part of quality control procedures.

No identifiers will be used in published reports.

### ***Will the study be conducted under a certificate of confidentiality?***

Yes, we will apply for the Certificate of Confidentiality

## **Direct Benefits to Subjects**

### **Direct Benefits to Subjects**

Participants will receive a free medical and psychiatric evaluation at baseline, and may benefit from improved symptoms of drug use from the behavioral treatment offered as part of the protocol, or from the medication. Patients will also be offered referrals upon completion of the study, or when they choose to leave. Patients found not to be eligible will also be offered referral opportunities should they wish.

## Compensation and/or Reimbursement

### Will compensation or reimbursement for expenses be offered to subjects?

Yes

**Please describe and indicate total amount and schedule of payment(s).**

**Include justification for compensation amounts and indicate if there are bonus payments.**

Incentive payments are provided to favor study retention and encourage participation in all aspects of the study, except medication intake.

Collection of vouchers will be contingent on attendance to all study appointments, the provision of a urine sample at every visit, completion of all self reports, and bringing the at-home medication for single-blind weighing.

For phase 1,

control participants will receive \$150 for their participation after they complete testing. After completion of Phase 1, they receive no further compensation.

cocaine-dependent patients will receive \$20/day, or will receive \$150 if they complete the whole week. Because availability of money can be a trigger to cocaine use, cocaine dependent patients will receive their reimbursement for phase 1 at the end of that week in a form of a voucher for services that can promote a drug-free lifestyle.

For Phase 2:

cocaine-dependent patients accumulate vouchers for completing all study procedures as described above. Each visit with completion of all study procedures will earn them \$5. They can also receive an extra \$20/week for each week of consecutive and complete participation. If

14. PROJECT DIRECTOR/PRINCIPAL INVESTIGATOR CONTACT INFORMATION
Prefix: Dr. * First Name: [name] Middle Name: N
* Last Name: [name] Suffix:
Position/Title: Research Scientist level VI
* Organization Name: Research Foundation for Mental Hygiene, Inc.
Department: 110 NYPI Substance Abuse Division:
* Street1: NYPI
Street2: [name]
* City: New York County / Parish: New York
* State: NY: New York Province:
* Country: USA: UNITED STATES * ZIP / Postal Code: 10032
* [contact] [contact]
* Email: [contact]

2) Cocaine Craving Scale (CCS, Weiss et al., 1997); 3) Subjective ratings of cocaine craving, depression, anxiety, stress during stress testing (Likert scale 0 to 10, 10 = worse) Physiological tests: 1) Nine drug urine toxicology (Iscreen™ 9 drugs); 2) Stress Sensitivity Testing: serum ACTH, HR, BP for Day 1 and Day 2 (see table 2.)

Phase 2 Measures: The goal of phase 2 is to test if IN OT can reduce relapse risk. Measures collected may inform *Primary Aim 2, Secondary Hypotheses, and Exploratory Aims a, b* (section 3.4). **Compliance monitoring:** a) Witnessed, and recorded insufflations of IN OT vs. Pbo, 3x/wk from a bottle kept refrigerated at STARS; b) Patients will be instructed on storing and using the nasal spray bottle before At-home insufflation begins. They will be told to bring this bottle with them at every visit. [*Monitoring: unbeknownst* to the patient, the at-home bottle will be weighed before being given, and will be weighed at every visit. The metered bottle delivers 5 IU/0.1cc or per puff. Each daily dose requires 4 puffs or 0.4 cc. The weight of each puff or 0.1cc is approximately 0.1g, hence for each at-home insufflation, the bottle weight is expected to change by 400 mg. The expected weight change will be compared to the actual recorded weight.] **Medical monitoring:** a) electrolyte: (Na, K, Cl), spot cortisol, urine pregnancy test for women at week 2, 4, 6; b) weekly medical review for signs and symptoms of hyponatremia and side effects. **Clinician Interviews:** 1) TLFB 3x/wk; 2) CGI-O 1x/wk; 3) Adverse event form 3x/wk; 4) HamD 1x/wk. **Self reports:** 1) PSS 1x/week, 2) CCS 3x/week. 3) subjective ratings of depression, anxiety, stress and cocaine craving (Likert scale 0 to 10) and BAS (table 2). **Physiological tests:** *Stress sensitivity testing:* repeat of Day 1 IN DDAVP 80 IU challenge, ACTH, HR, BP; 2) *Nine drug urine toxicology, 3x/wk.*

Study Assessments: (Table 1). **Physiological tests:** 1) *urine toxicology:* this will be estimated qualitatively at every visit by dipstick (Iscreen™, 9 drugs) which indicates the presence of cocaine, amphetamine, metamphetamine, cannabis, methadone, morphine, oxycodone, barbiturate, benzodiazepine. 2) *stress sensitivity testing:* as outlined in table 2, it is performed on two separate days, [in counterbalanced order.] Day 1: an endocrine challenge with IN DDAVP 80IU (de Goeij et al., 1991). After establishing baseline ACTH secretion, serum samples are taken at time points extending to 90 minutes. The DDAVP challenge is also repeated at the end of phase 2, to see if ACTH secretion is affected by 6 weeks of IN OT administration. Day 2 tests if pretreatment with IN OT treatment can acutely dampen the effect of DDAVP on ACTH secretion. After baseline is measured before and after IN OT, serum samples for ACTH are taken at time points extending to 90 minutes. Serum samples are spun, frozen at -20 Celsius, packed in dry ice, and shipped to the Nathan Kline Laboratory in Orangeburg, NY. 3) Medical monitoring: week 2,4,6: Na, K, Cl, CO3, spot cortisol, β-HCG for women. **Clinician Interviews:** 1) TLFB (Litten and Allan, 1992; baseline, each visit in phase 2). This is an adaptation of the alcohol TLFB, which estimates cocaine use in the past 30 days at baseline, and is then repeated at every visit with the aid of a calendar to obtain a day-by-day registry of cocaine use during phase 2. 2) CGI-O, (Guy, 1976; baseline, weekly during phase 2) the severity and improvement scales measure the overall clinical status of the subject and change from baseline. 3) BAS (Chaplin et al., 2010). This scale is used during stress sensitivity testing. Research staff rate participants on 13 items of behavior relating to arousal during the stress challenge. 4) Adverse event form is a check-list of side effects experienced by participants; 5) HamD, (Williams, 1988; baseline, each wk in phase 2). Estimates 25 depression symptoms. **Self reports:** 1) PSS (Cohen et al., 1983; baseline, weekly during phase 2) measures monthly situations in a subject's lives deemed stressful. Ten questions are scored between 0 (never) to 4 (very often). Modified, it will be administered weekly during phase 2, [and will include a open-ended question inquiring about any adverse life event in the past week.] 2) *Subjective ratings of cocaine craving, depression, anxiety, stress during stress testing (Likert scale 0 to 10, 10 = worse), performed during stress sensitivity testing.* 3) CCS (Weiss et al., 1997) 3-item questionnaire rating cravings for cocaine on a scale of 0 (none) to 9 (Strong).

3.3 Compensation and data management.

For phase 1, control participants will receive \$150 for their participation; cocaine-dependent patients will receive \$20/day, or will receive \$150 if they complete the whole week. [During phase 2, cocaine-dependent patients accumulate vouchers for completing all study procedures (Bringing home bottle, assessments, study visits).] Each visit with all study procedures completed will earn them \$5. They can also earn \$20 for each week of consecutive and complete participation. Transportation costs are covered (\$5/visit). Total earnings can reach \$450. StudyTrack, a software system for clinical trials will be used for data management.

3.4 Statistical Analysis:

3.4.1. Outcome measures: PHASE 1: **Primary outcomes:** 1) secretion of ACTH (continuous measure of area from the concentration-time curve (AUC) using trapezoid method, pg/mL/min). 2) subjective rating of cocaine craving, stress, depression, anxiety (continuous) 3) difference in ACTH secretion between IN DDAVP (day 1) and IN OT prior to IN DDAVP (day 2) (continuous measure); 4) difference in subjective rating of cocaine

craving, stress, depression, anxiety between IN VP (day 1) and IN OT prior to IN DDAVP (day 2; continuous, controlled for last day of use before entering Phase 1); **PHASE 2: Primary outcome:** 1) maximum number of consecutive abstinent days (continuous measure) ; **Secondary outcome:** 1) cocaine using days (continuous). **Covariates/Predictor Variables:** demographics, age, gender; cocaine data (TLFB, 30 days; IN vs. smoked).

3.4.2. Sample size: In PHASE 1, we will enroll a total of 100 participants: 1) Cocaine group (COC): Cocaine-dependent patients seeking treatment (n=50); 2) Control group (CON): Healthy matched controls (n=50), each matched demographically (see 3.1.1). In PHASE 2, we will randomize the 50 COC patients into two groups: 1) Oxytocin group (OT), n=25; 2) Placebo group (PBO), n=25. An independent statistician will perform, and an independent pharmacist will implement the randomization. Individuals will be stratified by route of cocaine use. The randomization will be balanced in blocks of random size 2 and 4 to prevent compromise of the blind.

3.4.3. Intent to Treat/ Dropouts and missing data: All primary analysis will be on Intent-to-Treat (ITT) sample, i.e. all subjects from COC and CON groups in Phase 1 (50 per arm) and all subjects randomized to OT and PBO groups in Phase 2 (25 per arm). [In Phase 1, we expect little attrition. Measures as described (3.4.1) will provide usable data after 2 days of measurements. For phase 2, we anticipate an attrition rate of 30%, leaving approximately 18 completers per arm.] If a patient drops out during Phase 2, the maximum number of consecutive abstinent days achieved in the trial will be considered as primary outcome. The inferences from analyses with missing data are considered valid provided that they are "missing at random" (Little and Rubin 1987). One can assume either parametric or semi-parametric models for missingness (Diggle and Kenward 1994; Kenward 1998; Liu et al 1999; Rotnitzky et al 1998). Inferences from various models of missingness provides a measure of the efficacy estimate from each models.

3.4.4. Significance testing and preliminary analyses: All tests for main effects will be performed at two-tailed significance $\alpha=5\%$. Before performing specific analyses (described below), we will examine all variables for outliers and normality. Demographic variables (ethnicity, gender, age) and baseline measures in the groups will be described in terms of means, standard deviations, proportions and 95% confidence intervals. The covariates (Section 3.4.1) will be included if they are found to affect outcome measures.

Hypotheses:

Primary Aim 1 [Phase 1]: The goal of primary aim 1 is to investigate the effect that both IN DDAVP and OT have on stress sensitivity. **Primary Aim 1a, hypothesis 1:** IN DDAVP will be associated with greater secretion of ACTH and subjective ratings in cocaine dependent patients compared to control patients. **Primary Aim 1b, hypothesis 2:** IN OT treatment will significantly reduce the secretion of ACTH and subjective ratings associated with IN DDAVP in cocaine dependent patients compared to control patients. The differences based on the outcomes specified in hypotheses 1 and 2 between the subjects in COC and CON groups will be examined using parametric or non-parametric matched sample test.

Primary Aim 2 [Phase 2]: The goal of primary aim 2 is to investigate the effect of OT on cocaine use after abstinence induction. **Primary Aim 2, hypothesis 1:** Cocaine-dependent patients receiving IN OT will display significantly more days of consecutive abstinence after abstinence induction compared with IN placebo at the end of the study. The effect of IN OT treatment (based on groups) on the primary outcome (maximum number of consecutive abstinence days for each patient) will be analyzed using generalized linear models (PROC GLIMMIX in SAS®) with main effect of randomization assignment (OT vs. PBO).

Secondary Hypotheses: We will examine the feasibility, safety, tolerability, and potential efficacy of IN OT for relapse prevention in cocaine dependence. 2.1): Cocaine-dependent patients receiving IN OT who complete all 6 weeks of phase 2 will tally fewer cocaine using days than placebo patients who complete all 6 weeks. 2.2): Cocaine-dependent patients receiving OT who relapse will tally fewer cocaine using days than patients receiving placebo who relapse. Regression analysis will be implemented using those who complete (2.1) and those who relapse (2.2) to test the effect of OT on the secondary outcome (cocaine using days).

Exploratory Aims: We will investigate a) if the acute reduction in stress sensitivity with IN OT in Phase 1 or at the end of Phase 2 (repeat IN DDAVP challenge) is associated with a greater number of days of continued abstinence from cocaine in Phase 2; b) if there are gender effects on the primary outcomes.

Power Analysis: **Primary aim 1:** With 50 cocaine dependent subjects and 50 matched controls, we have 50 matched pairs which give us at least 80% power to detect a significant difference between groups using 2-sided hypothesis test at a 5% level of significance for an effect size $\geq .41$. This is considered a small/medium effect size (Araya et al., 2006; Simeon et al., 2011), which are reasonable to expect based on the existing literature. **Primary aim 2:** In Phase 2, we randomize 50 participants into 2 groups (25 in PBO and 25 in OT). The comparison will achieve at least 80% power (testing 2-sided hypothesis of difference at 5% significance) when detecting an effect size ≥ 0.8 . This is a medium effect size that we based on existing relapse studies in cocaine dependence (Back et al., 2010).

Primary outcome:

The primary outcome was maximum number of consecutive cocaine abstinent weeks. Cocaine use was determined using urine toxicology and TLFB self-report. In a given week, cocaine use was defined as positive if any urine toxicology tests or TLFB self-report was positive (regardless if urine toxicology was negative or missing). Cocaine use was defined as negative if both urine toxicology and self-report were negative or if urine toxicology was missing, the self-report was negative. Cocaine use status was defined as missing if both urine toxicology and self-report were missing. Wilcoxon rank-sum tests were used to examine differences in maximum number of consecutive cocaine abstinent weeks by medication group.

Twenty-six cocaine patients were randomized to 6 weeks of Oxytocin (n=15) or Placebo (n=11). The median (IQR) of the maximum number of consecutive abstinent weeks was 1.0 (1.0 to 1.0) for the OT group and 1.0 (1.0 to 2.0) for the PBO group. The Wilcoxon rank-sum test was not significant, there was no effect of treatment arm on the maximum number of consecutive abstinent weeks ($W = 144.5, p = .67$).
